PROTOCOL: Probiotics for Chalaziosis Treatment in Children

Approval number: 07/19

Approved by CTS of Department of Medicine and Health Sciences “V. Tiberio” of Molise University on the 07 th January, 2019

The trial was registered at clinical trials.gov as NCT04322500 on the 25 th March, 2020 (“retrospectively registered”)

PURPOSE: Human gut holds over 100–1000 microbial species, which primarily modulate the host internal environment and thereby, play a major role in host health. Supplementation with probiotics has shown promising results against various enteric pathogens thanks to their unique ability to compete with pathogenic microbiota for adhesion sites, to alienate pathogens or to stimulate, modulate and regulate the host's immune response by initiating the activation of specific genes in and outside the host intestinal tract. [R. G. Kerry et al, *Benefaction of probiotics for human health: A review*, 2018] In recent years, intestinal microbiota emerged as a candidate responsible for providing innate stimuli to prime the immune system, and its contribution to pathogenesis of autoimmune diseases has been intensively studied. Clinical studies support a link between changes in gut commensal microbiota (‘dysbiosis’) and human autoimmune diseases including rheumatoid arthritis, spondyloarthritis, lupus, diabetes, inflammatory bowel disease and multiple sclerosis [McLean MH, Dieguez D Jr, Miller LM, et al. *Does the microbiota play a role in the pathogenesis of autoimmune diseases? Gut* 2015; Scher JU, Littman DR, Abramson SB. *Microbiome in inflammatory arthritis and human rheumatic diseases. Arthritis Rheumat* 2016; Ochoa-Reparaz J, Kasper LH. *The influence of gut-derived CD39 regulatory T cells in CNS demyelinating disease. Transl Res* 2017]. Moreover, animal studies on autoimmune uveitis in rodents have unraveled strong associations of gut microbiota with disease. Also ocular conditions such as chalazia are linked to dysbiosis [*Infective and Inflammatory Eyelid Disorders: Conventional and Unconventional Therapies to Maintain Eye Health and Avoid Lid Surgery*; A. L. Giacomini, *EC Ophthalmology* 2016]. Moreover, it is well known that any eating disorders such as excessive use of saturated fats, can result in a change in the composition of the secreted fat of the Meibomian glands, making it less fluid. So it becomes difficult to spill the glandular secretion leading to chalazia formation. The

correlation between inflammatory conditions of the conjunctival membrane, lacrimal dysfunctions and an intestinal immune condition featuring dysbiosis are pathophysiological conditions of great interest and are currently analysed. To the best of our knowledge there are no studies on probiotics supplementation in chalaziosis. Moreover, several evidence demonstrate that probiotics may play a role in the prevention and treatment of different conditions not only in adults, but also in children. In the latter population acute diarrhea is an important application of probiotics (Lactobacillus rhamnosus and Saccharomyces boulardii reduce the duration of gastroenteritis by approximately 24 h) [*The good bugs: the use of probiotics in pediatrics. Sansotta N, Curr Opin Pediatr.2019*]. Hence, this study aims to define the possible beneficial impact of probiotics on children suffering from chalaziosis.

DESIGN: This is a simple blind observational study. Paediatric patients affected by chalaziosis will be recruited. These patients will be divided in two groups, one receiving a supplementation with probiotics and the other one not. Prior to enrollment in the study all patients will undergo a complete ophthalmological examination which includes : visual acuity test, slit lamp for annexes and anterior segment assessment, ocular fundus examination, intra ocular pressure measurement. Subsequently a complete ophthalmological evaluation will be done weekly during the first month and then monthly until the healing. The ophthalmologist will be masked.

ATTENDED RESULTS: Altering the intestinal microbioma with specific probiotics can ameliorate the clinical course of chalaziosis by re-establishing intestinal and immune homeostasis. So, we expect to observe a reduction or absence of the recurrences of chalazia.

CONCLUSIONS: The use of probiotics for clinical health benefits is a fascinating area of research that the present era has yet to explore. Some of the elite properties of probiotics, such as anti-pathogenicity, anti-diabetic, anti-obesity, anti-inflammatory, anti-cancer, anti-allergic, and angiogenic activities and their effect on the brain and central nervous system are quite known. This study will provide further informations on probiotics and human health. Moreover, the intestinal microbiota are potentially crucial in spreading inflammatory disease of the eye, and can be targeted for therapeutic effects. So, throughout our study will be highlighted that probiotics supplementation could increase the effectiveness of traditional therapies in reducing recurrences of chalaziosis in an easy and feasible way.

Statistical Analysis Plan

Mann Whitney U test will be used in order to analyze if there will be a significant difference between the two groups in:

- Time taken for complete resolution of the chalazion
- Number of recurrences

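### The study is labelled observational yet divides children into probiotic and no-probiotic groups by an unstated method; unless allocation is random, the unadjusted test cannot credit a difference to probiotics

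*Combined protocol and SAP*

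**What the plan says.** The DESIGN section opens with the label: "This is a simple blind observational study". Shortly afterwards it describes how the groups come about: "These patients will be divided in two groups, one receiving a supplementation with probiotics and the other one not". It also provides for a masked assessor: "The ophthalmologist will be masked". Before enrolment each child has an eye examination, listed as "visual acuity test, slit lamp for annexes and anterior segment assessment, ocular fundus examination, intra ocular pressure measurement".

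The title block uses different language from the DESIGN label. The title presents probiotics as a treatment, and the registration statement calls the study a trial.

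The aim, at the end of the PURPOSE section, is that "this study aims to define the possible beneficial impact of probiotics on children suffering from chalaziosis". The CONCLUSIONS section goes further and anticipates that supplementation could make traditional therapies work better in reducing recurrences.

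The Statistical Analysis Plan is one sentence and two endpoints: "Mann Whitney U test will be used in order to analyze if there will be a significant difference between the two groups", applied to time to complete resolution and to number of recurrences.

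**The concern.** The label and the description point to different kinds of study. In an observational study the team records who takes probiotics. In a trial of a treatment the team assigns them. The wording about dividing the children could fit either, and it neither states nor excludes randomisation.

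This decides what the result can mean. Suppose children reached the probiotic group through a family's preference, a clinician's judgement or the order of attendance. The two groups may then have had different prospects of healing or recurrence from the start. An unadjusted comparison would carry that difference into both endpoints, where it could be reported as a probiotic benefit. A reader of the plan cannot tell whether this applies, so cannot tell how to read a significant p-value.

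**Working it through.** The plan gives no sample size, significance level, allocation ratio or outcome spread, so there is no figure to reproduce. The check is a comparison of the sections.

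1. **Is an allocation method stated anywhere?** No. The title block, PURPOSE, DESIGN, ATTENDED RESULTS, CONCLUSIONS and Statistical Analysis Plan contain no mention of randomisation, a sequence, a ratio, concealment, matching, or a rule such as parental or clinician choice. The DESIGN text shows no redaction or gap that would explain the omission.

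2. **Does other wording settle it?** No. The title block and the order of events in DESIGN (recruit, then divide) lean towards assignment by the study team. The observational label leans the other way. Even assignment by the team would not establish randomisation.

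3. **What does the test show in each case?** For either endpoint, the observed difference between groups can be split as

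   observed difference = probiotic effect + difference the groups would have shown without probiotics + chance.

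   Under random allocation the middle term has expectation zero; any imbalance that arises is part of chance, which the p-value allows for. Without random allocation the middle term is unknown, the p-value does not allow for it, and recruiting more children does not shrink it. The Mann-Whitney test addresses whether the outcome distributions differ. It cannot separate the first term from the second.

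4. **Does the plan contain anything that would deal with the middle term?**
   - Masking the ophthalmologist protects the assessment of healing and recurrence. It acts after the groups are formed and does not make them comparable.
   - The slit-lamp examination may supply baseline lid findings, but the Statistical Analysis Plan makes no use of them, and no listed item is said to predict healing or recurrence.
   - The PURPOSE section names diet as relevant: "excessive use of saturated fats, can result in a change in the composition of the secreted fat of the Meibomian glands", which it goes on to link to the formation of chalazia. Diet is not among the listed baseline examinations. The documents do not say whether it is recorded elsewhere, or that it affects healing time.
   - No baseline comparison, stratification or adjustment is planned.

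5. **Does the intended conclusion need the causal reading?** Yes. The Statistical Analysis Plan promises only a difference between groups, but the aim speaks of the impact of probiotics and the CONCLUSIONS section of increased effectiveness.

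6. **How large could the bias be?** This cannot be worked out. It would need the group sizes, the baseline imbalance and the strength of a prognostic factor, and none is given. Any simulated false-positive rate would rest entirely on invented inputs and would say nothing about this study, so none is offered as evidence.

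**The case against.** The strongest reply is that the proven defect is narrow: a conflicting label and a missing description. Dividing the children may simply be a loose way of saying that they were randomised, in which case a few sentences put it right. This stands, and it marks the limit of the point. A reader might infer that the children were not randomised, or that the comparison is biased. The documents support neither inference, because they are silent on the method.

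A second reply is that an observational study may legitimately have non-random groups. That is true, but such a study would need results worded as association and some account of baseline comparability. The plan has neither.

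A third is that the aim is hedged by speaking of a possible impact. The hedge concerns whether a benefit will be found, not whether a difference may be credited to probiotics, and the CONCLUSIONS section repeats the causal language.

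A fourth is that no confounder has been demonstrated. None has, and the link with diet is to formation of chalazia rather than to healing. But a plan that intends a causal conclusion has to say how its groups are made comparable, whether or not a reader can name the confounder.

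**Conclusion.** The point holds. The observational label, the division of recruited children into two groups and the treatment-trial language of the title block must be reconciled, and the allocation method must be stated. This has to be fixed, because the meaning of any result on either endpoint depends on it and cannot be recovered from the outcome data.

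The conclusion is conditional. If allocation is not random, the planned test cannot attribute a difference to probiotics. If it is random, the confounding objection falls away. No magnitude can be attached to the bias, and the seriousness of the point does not rest on one.

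A reader might also infer that, once randomisation is confirmed, the Statistical Analysis Plan is sound. The documents do not support that either. Visits are scheduled only until healing, no follow-up period for recurrences is defined, and nothing says how children who never heal or who leave are handled. Randomisation resolves none of these.

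**What to change.** Apply whichever case is true.

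1. **Enrolment is still open.** Replace the DESIGN wording on dividing the children with: *will be randomly allocated from a computer-generated list, concealed until enrolment and from the masked ophthalmologist*. State the ratio and delete the word observational. Cost: a protocol amendment with its approval, and a list holder other than the ophthalmologist; if families could choose before, they no longer can. This route may have closed: approval was given "on the 07 th January, 2019" and registration in March 2020 was retrospective. Any children already divided without randomisation belong under case 3.

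2. **Children were already randomised.** State the method, ratio and concealment, and delete the word observational. Cost: a few sentences. This removes the confounding objection only.

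3. **Children were divided without randomisation.** State the rule used, tabulate the recorded baseline findings by group, and word results and conclusions as association rather than effect. Only if prognostic baseline factors were recorded, add an adjusted or stratified comparison of both endpoints, on factors named before outcomes are compared by group. Cost: text, one table, possibly one further analysis, and a weaker conclusion. Factors that were not recorded, which may include diet, cannot be corrected for, and small groups would support only a few strata.

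No case needs extra visits.

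### The planned conclusion is that probiotics add to traditional therapies, but nothing makes those therapies equal between groups and the Mann-Whitney test is unadjusted, so an outcome-relevant therapy imbalance would be read as a probiotic effect or hide one

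*Combined protocol and SAP*

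**What the plan says.** - DESIGN gives the design type: "This is a simple blind observational study".
- DESIGN forms the groups by supplement alone: "These patients will be divided in two groups, one receiving a supplementation with probiotics and the other one not". It gives no allocation method, names no traditional therapy, does not require the same therapy in both groups, and does not plan to record therapy.
- DESIGN has one safeguard: "The ophthalmologist will be masked". It sets the visits: "a complete ophthalmological evaluation will be done weekly during the first month and then monthly until the healing".
- CONCLUSIONS states the claim the study hopes to support: "probiotics supplementation could increase the effectiveness of traditional therapies in reducing recurrences of chalaziosis". Traditional therapies appear nowhere else as part of the study.
- The SAP is one method for two outcomes, time to complete resolution and number of recurrences: "Mann Whitney U test will be used in order to analyze if there will be a significant difference between the two groups in". It has no covariate or stratification factor.

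**The concern.** A claim that a supplement adds to existing therapy needs that therapy to be alike in both groups, or an analysis that allows for it. The plan provides neither. By its own wording, traditional therapies act on recurrences, which is one of the two outcomes, so therapy is a prognostic factor. With no random allocation stated, balance cannot be expected even on average.

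If more supplemented children receive the better therapy, the trial can report a benefit that the probiotic did not produce. If the imbalance runs the other way, it can miss a real benefit. The Mann-Whitney test uses only the outcome and the group label, so it cannot separate these cases from a true effect. Therapy is one possible confounder among several; it is singled out because the planned conclusion is about adding to it.

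**Working it through.** The plan gives no sample size, healing time, recurrence rate or therapy share, so it has no figure to reproduce. Every numerical input below is an assumption, except the visit schedule, which comes from DESIGN.

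**Step 1: what the test targets.** Let pT and pC be the shares of supplemented and control children on the better of two therapies. Let θ be the probability that a child on the better therapy does better than a child on the other, with ties counted half. With no probiotic effect, the Mann-Whitney probability that a supplemented child does better is

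P = 0.5 + (pT − pC)(θ − 0.5).

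P equals 0.5 only if the shares match or therapy does not affect the outcome (θ = 0.5). So a therapy difference matters only if it is both unbalanced and outcome-relevant.

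**Step 2: numbers for a 20-point gap.** Healing times are taken as exponential and read at the next visit (weeks 1–4, then every 4 weeks). Recurrences are taken as Poisson.

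| Assumed contrast, better vs other therapy | θ | P |
|---|---|---|
| Resolution, medians 3 vs 9 weeks | 0.746 | 0.5 + 0.2 × 0.246 = 0.549 |
| Resolution, medians 4 vs 8 weeks | 0.664 | 0.5 + 0.2 × 0.164 = 0.533 |
| Recurrences, means 0.2 vs 0.6 | 0.642 | 0.5 + 0.2 × 0.142 = 0.528 |
| Recurrences, means 0.3 vs 0.6 | 0.604 | 0.5 + 0.2 × 0.104 = 0.521 |

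**Step 3: false-positive rate of the planned test by simulation.** No probiotic effect, 50 per group, shares 0.5 ± half the gap, two-sided 5% level, 10,000 runs.

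| Contrast | Gap 0 | 10 points | 20 points | 30 points |
|---|---|---|---|---|
| Resolution 3 vs 9 | 4.8% | 7.6% | 13.8% | 25.1% |
| Resolution 4 vs 8 | 4.9% | 5.9% | 8.5% | 13.9% |
| Recurrences 0.2 vs 0.6 | 5.2% | 5.6% | 9.1% | 14.3% |
| Recurrences 0.3 vs 0.6 | 4.8% | 5.4% | 7.0% | 9.9% |

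A van Elteren test stratified by therapy stays between 4.6% and 5.3% in every cell. Repeat runs with separate code agree within simulation error; the lowest of the four 20-point results came out near 6% in one repeat, hence the range of about 6–14%.

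**Step 4: sensitivity at a 20-point gap.**
- With 25 per group, the plain test gives 9.3%, 5.6%, 6.3% and 6.0%, in the order of the table. With 100 per group it gives 22.8%, 12.7%, 13.5% and 9.5%.
- With a milder contrast (4 vs 6 weeks; 0.4 vs 0.6 recurrences) and 50 per group, it gives about 6%.
- A different model (log-normal healing times, better therapy multiplying time by 0.5 or 0.7, shares 50% vs 70%, 50 per group) gives 16.2% and 8.5%.

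**Step 5: the opposite imbalance.** The probiotic truly halves the healing time or the recurrence rate, with 50 per group and 6,000 runs.

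| Contrast | Therapy balanced: plain / stratified | Controls 20 points higher on better therapy: plain / stratified |
|---|---|---|
| Resolution 3 vs 9 | 73.5% / 82.4% | 40.9% / 80.0% |
| Recurrences 0.2 vs 0.6 | 39.8% / 42.6% | 20.9% / 40.1% |

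**Step 6: what stratifying costs and what it cannot do.** If therapy is irrelevant and balanced, power is 83.1% plain vs 82.3% stratified (resolution, median 5.5 weeks) and 42.5% vs 42.3% (recurrences, 0.4 per child). If baseline severity rather than therapy drives the same contrast, the therapy-stratified test gives 7.1%, 13.6% and 25.0% at gaps of 10, 20 and 30 points (3 vs 9 weeks), no better than the plain test at 6.9%, 13.8% and 25.3%.

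The recurrence figures also assume equal, complete observation of every child. DESIGN schedules visits only up to healing, so the plan does not define such a window.

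**The case against.** The strongest reply is that usual therapy for every child is probably intended. The word supplementation suggests it, the aim at the end of PURPOSE is simply the benefit of probiotics in these children, and the add-on sentence is hopeful rather than a formal hypothesis. This stands in part. A reader might infer that therapy does differ between groups, or that any difference would bias the result. The documents support neither: they do not mention two therapies of unequal efficacy, and a difference that does not affect the outcome does no harm.

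Masking is a second reply. If the masked ophthalmologist also sets therapy, the choice cannot follow a known group. That is a possible safeguard, but DESIGN does not say who prescribes. Masking the examiner does not equalise therapy already in use at enrolment, and no masking of families is described.

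Third, the root gap is the absence of random allocation, which would address therapy, severity and diet together. That is correct. PURPOSE itself points to diet: "any eating disorders such as excessive use of saturated fats, can result in a change in the composition of the secreted fat". Stratifying by therapy is a partial remedy only, as Step 6 shows.

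Fourth, the sizes are assumed, and the four main contrasts are two- to threefold. This also stands. At a 10-point gap the rate is only about 5–8%, and mild contrasts or 25 per group give little inflation.

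**Conclusion.** The point holds in conditional form. The plan intends an add-on conclusion, is called observational, states no random allocation, does not require equal therapy and uses an unadjusted test. If outcome-relevant therapy differs between groups, the test would attribute that difference to the probiotic or mask a real effect.

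It would go too far to say that the trial will report a false benefit. Whether therapy differs is unknown, and the size rests entirely on assumed therapy effects, shares and group sizes. For 50 per group and a 20-point gap, the false-positive rate is about 6–14% instead of 5%. The reverse gap cuts power from about 73% to 41% for resolution time and from about 40% to 21% for recurrences, in the stronger contrasts. The gap in the plan is certain and its consequence is conditional, so this is a change that should be made rather than a fatal flaw.

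**What to change.** 1. In DESIGN, give both groups the same named traditional therapy. Where the investigators assign the supplement, set the therapy before the child's group is known. Record therapy at enrolment for every child.
2. If more than one therapy is in use, or children are already treated, replace the plain Mann-Whitney test for both outcomes. Suggested SAP text: *Each outcome will be compared between groups with a van Elteren test stratified by traditional therapy at enrolment; therapy will be reported by group.* Do not stratify on changes made after enrolment; record these with dates and report them by group.
3. Limit the conclusion to the probiotic given on top of that therapy. State that, without random allocation, severity, diet and other confounders remain uncontrolled.

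**Cost.** The change needs one recorded field and a standard rank test, with no extra patients or visits, and about 0–1 point of power if therapy is irrelevant. There is less freedom to vary therapy by child, and a therapy used in only one group contributes no information. The trial was "retrospectively registered", so some children may already have been treated. For them, therapy cannot be fixed in advance and would have to be taken from clinical notes. If supplement use is merely observed, setting therapy before the group is known is not possible, and items 2 and 3 carry the remedy.

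### Time to complete resolution is an event time, but the SAP tests it with a plain Mann-Whitney U and sets no cut-off, censoring method or rule for children not seen healed

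*Combined protocol and SAP*

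**What the plan says.** The DESIGN section has children examined "weekly during the first month and then monthly until the healing". It sets up two groups, "one receiving a supplementation with probiotics and the other one not", and on masking says only "The ophthalmologist will be masked".

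The Statistical Analysis Plan is one sentence with two bullets. It says that a "Mann Whitney U test will be used in order to analyze if there will be a significant difference between the two groups in" two outcomes. The first is "Time taken for complete resolution of the chalazion"; the second is the number of recurrences.

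Neither part gives a maximum follow-up, an analysis cut-off, a censoring method, or a rule for a child who leaves before healing is seen or is unhealed at closure. No sample size, significance level, healing time or expected loss is stated.

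**The concern.** Mann-Whitney needs one rankable value per child. A child not seen healed has no healing time, only a lower bound on it. Without a rule, the analyst must exclude the child, enter the last visit as the healing time, or assign the worst rank. These choices can move the comparison in different directions, and the choice could be made after the data are seen.

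Unequal loss is possible here: one group receives a supplement and the other does not, no placebo is mentioned, and no masking of families is described. At stake are a false difference in healing time if loss is clearly unequal, and lost power even if it is equal.

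**Working it through.** The plan has no figure to reproduce, so the check asks how each handling behaves when the groups truly do not differ.

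**Inputs.** From the DESIGN section: weekly visits for a month, then monthly (taken as days 7, 14, 21, 28, then every 30 days). Assumed: 30 per group, two-sided 5% test, exponential healing with a median of 62 days in both groups, 4000 simulated trials per case. The Monte Carlo standard error at 5% is √(0.05 × 0.95 / 4000) = 0.3 points.

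**Direction, by hand, loss spread over follow-up.** Let healing have hazard h, and let loss be independent and exponential with fraction l lost before healing. Observed healing times among healed children then have rate h/(1 − l). Take l = 0.10 and 0.40 and ignore rounding to visits.

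- Exclusion: the chance that a healed child in the lower-loss group has the shorter time is (1/0.9) / (1/0.9 + 1/0.6) = 1.111/2.778 = 0.40, not 0.50. The higher-loss group looks faster.
- Last visit: the same 0.40, now on all 30 children per group instead of an expected 27 and 18. Rounding lost children down to a visit adds to the shift.
- Worst rank: the chance that the lower-loss child ranks better is 0.9 × 0.4 + 0.9 × 0.6 × 0.40 + 0.5 × 0.1 × 0.4 = 0.36 + 0.216 + 0.02 = 0.596. The higher-loss group looks slower.

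**Direction, by hand, children who never return after baseline.** Healing times among those who remain are unaffected, so exclusion gives 0.50. Worst rank gives 0.36 + 0.54 × 0.5 + 0.02 = 0.65 in favour of the lower-loss group. Last visit (time zero) gives 0.65 in favour of the higher-loss group.

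**Simulated false positives, unrelated loss spread over follow-up.**

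| Lost | Exclusion | Last visit | Worst rank |
|---|---|---|---|
| 10% vs 20% | 6.7% | 7.8% | 7.2% |
| 10% vs 30% | 10.9% | 17.0% | 13.6% |
| 10% vs 40% | 17.4% | 34.7% | 26.8% |

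At 20 to 50 per group, log-rank stays at 4.5–6.1% and Gehan-Wilcoxon at 4.5–6.0%. At 10% vs 40%, 99.7% (exclusion) and 100% (last visit) of false positives favour the higher-loss group; with worst rank, none do. A second simulation with a 13-week median and 15, 25 and 50 per group gave the same pattern at 10% vs 40%: exclusion 10.3%, 17.9%, 31.3%; last visit 21.8%, 34.3%, 61.4%; log-rank 5.0%, 4.8%, 5.7%.

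**Early unrelated loss** (at baseline or within 28 days; 10% vs 30% or 40%). Exclusion gives 3.9–7.0%, last visit and worst rank about 22–55%, log-rank 5.0–6.0%.

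**Where type I error holds.** All followed to healing: Mann-Whitney 4.7%. Equal loss of 10–30%: 4.5–5.9% for every method. Closure equal in both groups (180-day cut-off, or follow-up spread over 90–270 days): 4.5–5.7%.

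**Power, medians 45 vs 90 days.** Full follow-up: Mann-Whitney 60%, Gehan-Wilcoxon 61%. Equal loss hazards averaging 20% lost: best Mann-Whitney version 45%, Gehan-Wilcoxon 52%, log-rank 62%. Equal closure: excluding unhealed children 21–22%, worst rank 56–60%, Gehan-Wilcoxon 57–61%, log-rank 66–69%.

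**Loss related to healing.** If healed children skip the confirming visit, 10% vs 40%: exclusion 4.9%, last visit 6.3%, worst rank 52.4%, Gehan-Wilcoxon 18.5%, log-rank 21.7%. Counting those children as healed at the next scheduled visit brings log-rank to 5.7%. If slow healers leave after day 28, 10% vs 50% of them: 13%, 27%, 10%, 7% and 8% in the same order.

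**The case against.** Followed as written, the schedule gives every child a healing time, and Mann-Whitney is then valid. Equal loss does not disturb its type I error either, and a 10-point gap matters little. Both groups appear to share one visit schedule, and the CONCLUSIONS section says "probiotics supplementation could increase the effectiveness of traditional therapies in reducing recurrences of chalaziosis", which may mean that both groups receive usual treatment. All of this stands. A reader might infer that unequal loss is expected here, or that the planned test is invalid. The documents support neither; they only leave the possibility open.

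A reader might also infer that every way of handling unequal loss distorts the result. That is too broad. Exclusion, the natural default for a missing value, stays near 5% when unrelated loss comes early, and the documents say nothing about when loss would occur.

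The log-rank test is not a cure. If healed children skip the confirming visit at unequal rates, it does worse than exclusion or last-visit handling (34.2% against 5.2% and 8.0% at 50 per group, 10% vs 40%). The documents do not show which kind of loss is likelier.

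Part of log-rank's power advantage comes from assuming exponential healing. With log-normal times and full follow-up, Mann-Whitney has 71% and log-rank 69%.

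What survives is the gap itself: the plan does not say how a child not seen healed enters the analysis, and a standard method would settle it in advance.

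**Conclusion.** The point holds in a limited form and should be fixed, with medium confidence. The omission is certain from the text; its consequence depends on loss that the documents do not quantify. The false-positive risk needs a gap of about 20 points or more. For unrelated loss spread over follow-up it is then roughly 11–17% at 10% vs 30% and 17–35% at 10% vs 40%, with 30 per group. Last-visit and worst-rank handling err in opposite directions whenever the loss occurs; exclusion errs only when loss is spread over follow-up. With equal loss or closure the cost is power alone.

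Every rate rests on assumed sample size, healing times, and amount and timing of loss. A reader might take this as undermining the trial's main expectation. It does not: ATTENDED RESULTS says "we expect to observe a reduction or absence of the recurrences of chalazia", and this point concerns only the other listed outcome.

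**What to change.** For this endpoint, replace Mann-Whitney by one pre-specified censored-data test: log-rank, with Kaplan-Meier medians and a Cox hazard ratio with 95% CI. Gehan-Wilcoxon, the direct extension of Mann-Whitney to censored data, is acceptable if named in advance instead. Set time zero at enrolment, state one analysis cut-off, and censor children not seen healed at their last masked visit. State that healing is known only to the visit interval.

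Record the reason for each loss and report loss by group. Pre-specify a sensitivity analysis that counts a child recorded as stopping because the lid looked clear as healed at the next scheduled visit. Apply it only where that reason is recorded: counting every lost child as healed gives about 26% false positives when unrelated loss is 10% vs 40%.

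The cost is a few SAP sentences, one data field per lost child and standard software, with no extra visits. The downside is that the primary test assumes loss unrelated to healing. If healed children skip the confirming visit at unequal rates, it is biased and can be worse than exclusion. The sensitivity analysis relies on reports from families who are not described as masked; if 30% of unrelated losses were wrongly recorded as clear lid, log-rank would give 7.5–8.6% at 10% vs 40%.
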